6.2.1. Tabulation by eGFR Assessment Time Point

When tabulating the eGFR at each assessment time point, data that fall within the allowable time windows defined in “Table 6.2: Test/Observation Schedule Allowable Time Windows” will be used. For data that have been reported as having been collected at treatment period discontinuation, data that were collected within the allowable time window for the day of treatment period discontinuation will be used. Although a data tabulation at discontinuation will not be performed, data that have been collected within the allowable time window for the day of treatment period discontinuation that are also within the allowable time window for the time point in question will as a rule be used as data for that time point. In addition, if multiple measurements have been taken within an allowable time window, data from the test that was performed on the day closest to the target day will be used. If there are multiple measurements, and the difference in the numbers of days between the day of each measurement and the target day are the same, then the data that were collected earlier will be used.

6.2.2. Tabulation of the eGFR at Each Assessment Time Point When Imputing Data Outside the Allowable Time Window

When tabulating the eGFR data for each assessment time point, the data stipulated in 6.2.1 will be combined with data imputed by means of multiple imputation (██████████) for data for which the assessment time point was outside the allowable time window. A linear regression model with the data at each assessment time point from the first day of the treatment period until Week 88 of the treatment period as the explanatory variable will be used to replace missing values for each assessment time point from Week 4 of the treatment period through Week 104 of the treatment period. It will be assumed that the pattern of missing values is non-monotonic.

6.2.3. Tabulation of Endpoints Other Than the eGFR and Urine ACR at Each Assessment Time Point

When tabulating the data for endpoints other than the eGFR and urine ACR, data that have been collected within the allowable time windows defined in “Table 6.2: Test/Observation Schedule Allowable Time Windows” will be used. For data that have been reported as having been collected at treatment period discontinuation, data that were collected within the allowable time window for the day of treatment period discontinuation will be used. Although a data tabulation at discontinuation will not be performed, data that have been collected within the allowable time window at discontinuation that are also within the allowable time window for the time point in question will be used as data for that time point. Data will not be replaced with data from outside the allowable time windows. In addition, if multiple measurements have been taken within an allowable time window, data from the test that was performed on the day closest to the target day will be used. If the differential number of days from the

reference date is equal, the data obtained before the reference date will be used to evaluate efficacy, and the data obtained after the reference date will be used to evaluate safety.

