8.4 Duration of Study

- (1) Run-in period : 2 weeks
- (2) Treatment period : 104 weeks

Rationale

(1) Run-in period

A single-blind run-in period with placebo administration was established in order to confirm the eligibility of the subjects for participation in the study.

(2) Treatment period

It was reported as a result of a meta-analysis of multiple clinical studies in patients with chronic nephropathy that there is a correlation between the proportion of patients with a 30% decline in the eGFR after 2 years and the proportion of patients with end-stage kidney disease.¹⁶⁾ It has also been reported that there is a similar relationship in Japanese, as a result of an analysis of a cohort study that was conducted in Japan (CKD-JAC),¹⁷⁾ and the company therefore chose the proportion of subjects with a 30% decline in the eGFR after 2 years as the primary endpoint because the company believed that this could be used as a surrogate endpoint.

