HbA1c	Hemoglobin A1c
hCG	Human chorionic gonadotropin
HDL-C	High density lipoprotein cholesterol
HIV	Human Immunodeficiency Virus
LOCF	Last observation carried forward
NSAID	Non-steroidal anti-inflammatory drugs
NYHA	New York Heart Association
PPS	Per Protocol Set
PTP	Press-through sheets
PVD	Peripheral Vascular Disease
SGLT	Sodium glucose co-transporter
SMBG	Self-monitoring of blood glucose
t _{1/2}	Terminal elimination half-life
t _{max}	Time to reach maximum plasma concentration

Definition of Terms

Term	Definition
Screening period	The period from the first day of the screening period until the completion of the scheduled tests on the first day of the run-in period, 4 weeks at most.
Run-in period	The 2-week period from the completion of the scheduled tests on the first day of the run-in period until the completion of the scheduled tests on the first day of the treatment period.
Treatment period	The period from the completion of the scheduled tests on the first day of the treatment period until the completion of the scheduled tests on the last day of the treatment period (Week 104 of the treatment period or the day of treatment period discontinuation).
Follow-up observation period	The 4-week period from the completion of the scheduled tests on the last day of the treatment period.
Pre-treatment period discontinuation	Discontinuation in the period between informed consent acquisition and the end of the run-in period.
Treatment period discontinuation	Discontinuation during the treatment period
Proportion of subjects achieving a 30% decline in the eGFR	The proportions of subjects at the end of the treatment period with a decline of 30% in the eGFR or more compared to the average of the values on the first days of the run-in and treatment periods
Proportion of subjects achieving a 40% decline in the eGFR	The proportions of subjects at the end of the treatment period with a decline of 40% in the eGFR or more compared to the average of the values on the first days of the run-in and treatment periods

1. Introduction

This document describes the sponsor's plans for the statistical analyses in the "a randomized, double-blind, placebo-controlled study to evaluate efficacy and safety of canagliflozin (TA-7284) in patients with diabetic nephropathy," and covers the information that is included in the study protocol, but in greater detail.

[figure not shown]
2. Study Objective And Study Design

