3.1. Efficacy Endpoints

3.1.1. Primary endpoint

Proportion of subjects achieving a 30% decline in the eGFR (The proportions of subjects at the end of the treatment period with a decline of 30% in the eGFR or more compared to the average of the values on the first days of the run-in and treatment periods)

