5.2. Safety Analysis Sets

The analysis sets consisting of all randomized subjects other than the following constitute the safety analysis sets.

- All subjects who did not take the investigational product at all
- All subjects for which no post-randomization safety data are available

6. Handling of Data

The data handling procedures are described below, except for issues that are determined by the study sponsor's case review board.

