6.1. Handling of Missing Values

When test values are missing or reported as reference data, or can not be measured because of, for example, a problem with the test sample, this parameter will be handled as missing. If the data (e.g., test

values) required for derivation include even 1 missing or uncollected value, the derived variable will be considered missing.

6.2. Handling of Time Point Data When Tabulating the Data by Evaluation Time Point

Table 6.2: Test/Observation Schedule Allowable Time Windows

Assessment Time Point		Reference Date	Allowable Window
Screening period	First day of the screening period	—	*1
Run-in period	First day of the run-in period	-14 days	-17 days to -11 days
Treatment period	First day of the treatment period* ² (Week 2 of the run-in period)	0 days	—
	Week 4 of the treatment period	28 days	14 days to 42 days
	Week 8 of the treatment period	56 days	43 days to 70 days
	Week 12 of the treatment period	84 days	71 days to 98 days
	Week 16 of the treatment period	112 days	99 days to 126 days
	Week 20 of the treatment period	140 days	127 days to 154 days
	Week 24 of the treatment period	168 days	155 days to 182 days
	Week 28 of the treatment period	196 days	183 days to 210 days
	Week 32 of the treatment period	224 days	211 days to 238 days
	Week 36 of the treatment period	252 days	239 days to 266 days
	Week 40 of the treatment period	280 days	267 days to 294 days
	Week 44 of the treatment period	308 days	295 days to 322 days
	Week 48 of the treatment period	336 days	323 days to 350 days
	Week 52 of the treatment period	364 days	351 days to 378 days
	Week 56 of the treatment period	392 days	379 days to 406 days
	Week 60 of the treatment period	420 days	407 days to 434 days
	Week 64 of the treatment period	448 days	435 days to 462 days
	Week 68 of the treatment period	476 days	463 days to 490 days
	Week 72 of the treatment period	504 days	491 days to 518 days
	Week 76 of the treatment period	532 days	519 days to 546 days
	Week 80 of the treatment period	560 days	547 days to 574 days
	Week 84 of the treatment period	588 days	575 days to 602 days
	Week 88 of the treatment period	616 days	603 days to 630 days
	Week 92 of the treatment period	644 days	631 days to 658 days
	Week 96 of the treatment period	672 days	659 days to 686 days
	Week 100 of the treatment period	700 days	687 days to 714 days
	Week 104 of the treatment period	728 days	715 days to 742 days

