Treatment period discontinuation		The day of treatment period discontinuation	Within 7 days of the day of treatment period discontinuation
Week 4 of the follow-up observation period		Week 104 of the treatment period (or the day of treatment period discontinuation)	28 to 42 days after the last day of the treatment period

*1: The first day of the run-in period should be within 4 weeks of the first day of the screening period.

*2: The first day of the treatment period is the day of the initial prescription of the treatment period investigational product.

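### The SAP's window rules let possibly non-fasting discontinuation samples and off-treatment follow-up eGFR values stand in for scheduled data, and no 30% or 40% decline analysis uses a discontinuation eGFR taken before day 715

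*SAP*

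**What the plan says.** - **Windows.** SAP 6.2.1 takes eGFR values lying inside a Table 6.2 window as the data for that time point. For the discontinuation visit, "data that have been collected within the allowable time window for the day of treatment period discontinuation that are also within the allowable time window" of the time point concerned are, as a rule, its data. Table 6.2 gives Week 88 days 603-630, Week 92 "631 days to 658 days", Week 96 days 659-686, Week 100 days 687-714 and Week 104 days 715-742. The follow-up visit is due "28 to 42 days after the last day of the treatment period".
- **Imputation.** SAP 6.2.2 uses a linear regression model with the values "from the first day of the treatment period until Week 88 of the treatment period as the explanatory variable". The name of the imputation method is redacted.
- **Endpoint.** SAP 3.1.1 defines it as "The proportions of subjects at the end of the treatment period with a decline of 30% in the eGFR or more", relative to the two-value baseline. The SAP's definition of terms runs the treatment period to "the last day of the treatment period (Week 104 of the treatment period or the day of treatment period discontinuation"). Protocol 9.2.3.1 requires an eGFR at discontinuation. Protocol 8.4 describes "the proportion of subjects with a 30% decline in the eGFR after 2 years as the primary endpoint", and Protocol 13.3.2 prescribes multiple imputation and leaves sensitivity analyses to the SAP.
- **Analyses.** SAP 7.6.1.1 and 7.6.1.2 use the imputed Week 104 data. Other Analysis 1 (7.6.1.3, through 6.3) counts a missing Week 104 value as a decline. Other Analysis 2 (7.6.1.4) uses in-window data only. SAP 7.6.2.1 repeats all four for the 40% decline.
- **Fasting.** Protocol 8.6.2 and the schedule notes in SAP 2.4.1 exempt the discontinuation visit from the 10-hour fast. Protocol 9.2.3.9, 9.2.3.11 and 9.2.3.13 nevertheless ask for glucose, lipids and the urine glucose/creatinine ratio there when possible. SAP 6.2.3 places in-window discontinuation values at the scheduled time point without mentioning fasting.
- **Reserve.** SAP section 6 says: "The data handling procedures are described below, except for issues that are determined" by the sponsor's case review board.

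**The concern.** Each gap lets a measurement be used, or left unused, in a way the endpoint's name does not suggest.

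- A glucose or triglyceride value taken after a meal would be analysed as fasting in the repeated-measures models of SAP 7.6.2.2 and 7.6.2.3.
- An eGFR drawn about four to six weeks after treatment ended could be analysed as the Week 104 value. Protocol section 1(2) describes a rapid, slight, hemodynamic lowering of eGFR on TA-7284, so an off-treatment value may not represent the on-treatment state. Protocol 5.2 gives the follow-up period the separate purpose of watching eGFR after treatment.
- Worsening of the primary disease is a listed reason for discontinuation (Protocol 12.1). For such a subject the discontinuation eGFR is the last treatment-period measurement of the primary variable. None of the planned analyses shows the result when that value decides the classification.

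**Working it through.** The documents give no figure to reproduce here. Protocol 12.2 dates discontinuation to the day of the discontinuation evaluations where these are done, so I write *d* both for the day of the discontinuation sample and for the last day of the treatment period.

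**1. Where a discontinuation eGFR lands (Table 6.2).**
- Days 715-742: it is the Week 104 value and does classify the subject.
- Up to day 630 (end of the Week 88 window): if it lies in a window, it can at most inform the imputation.
- Days 631-714 (Weeks 92, 96 and 100): 3 × 28 = 84 days, and 84/728 = 11.5% of the treatment period. It is neither a Week 104 value nor a stated regressor.

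**2. How each analysis treats a subject with a discontinuation value before day 715 and no Week 104 value.**
- 7.6.1.1 and 7.6.1.2: imputed.
- 7.6.1.3: a decline, whatever was measured.
- 7.6.1.4: no Week 104 value to use.
- 7.6.2.1: the same three outcomes at 40%.

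**3. When a follow-up eGFR reaches the Week 104 window.** The sample falls on day *d*+28 to *d*+42; the window is 715-742.
- Possible if *d*+42 ≥ 715 and *d*+28 ≤ 742, so *d* = 673 to 714 (42 days).
- Certain, for an in-window follow-up sample, if *d*+28 ≥ 715 and *d*+42 ≤ 742, so *d* = 687 to 700 (14 days).
- SAP 9.2 mentions a 735-day maximum for Week 104. With that limit the ranges become 673-707 and 687-693; the point is unchanged.

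For these leavers the discontinuation sample lies in the Week 96 or Week 100 window and is set aside, while the later off-treatment sample could be taken as Week 104 data. Through 6.2.1 it would reach all four decline analyses and the eGFR mixed model. In Other Analysis 1 it would also replace the automatic decline.

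**4. Numbers of subjects.** The documents give no discontinuation rate. Assume 10-20% of 300 (30-60 subjects), spread evenly over 728 days.
- Fasting values per 28-day window: 30-60 × 28/728 = 1.2-2.3 subjects. Week 104 (days 715-728): 30-60 × 14/728 = 0.6-1.2. These are upper limits, since the samples are taken only when possible and may be fasting.
- Follow-up overlap, days 673-714: 30-60 × 42/728 = 1.7-3.5 subjects at most.
- Days 631-714: 30-60 × 84/728 = 3.5-6.9 subjects.
- Leaving before day 715: 30-60 × 714/728 = 29.4-58.8 subjects, or 9.8-19.6% of 300.

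**The case against.** The strongest reply is that the plan chose Week 104 deliberately. The analysis parameter is Week 104 throughout SAP 7.6.1, SAP 6.3 treats end-of-treatment eGFR as Week 104 data, Protocol 8.4 speaks of two years, and Protocol 13.3.2 requires imputation. If the discontinuation value settled the outcome, there would be little left to impute. This stands. A reader might infer that the primary analysis breaches the protocol's endpoint; the documents do not support that, because they carry both readings and expressly provide for imputation.

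A reader might also infer that discontinuation eGFRs are never used. That is too strong: a value on days 715-742 classifies the subject, and earlier in-window values up to Week 88 can inform the imputation. Other Analysis 1 also counts a subject with a late fall and no Week 104 value as a decline, though it does the same for every such subject. ESRD and creatinine doubling remain secondary events. Classifying by the discontinuation value is itself a last-value rule with a bias of its own.

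On the follow-up sample, the SAP defines follow-up as a separate period, gives it its own row in Table 6.2 and reports it as Week 108. That is probably the intention, but 6.2.1 selects by day and states no exclusion.

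On fasting, exemption does not show that any sample was non-fasting. The case review board could act, and SAP 6.1 treats values reported as reference data as missing. Neither provision is tied to fasting status.

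**Conclusion.** The point holds as three limited gaps.

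- **(a) Fasting.** Possibly non-fasting discontinuation values can enter fasting-endpoint models under the rule as written. Few subjects are involved, and the effect on means cannot be derived.
- **(b) Follow-up eGFR.** Read literally, 6.2.1 admits an off-treatment sample as Week 104 data for leavers on days 673-714. The day ranges follow from Table 6.2 alone.
- **(c) Discontinuation eGFR.** No 30% or 40% analysis classifies a subject by a value taken before day 715, although the defined treatment period can end on the day of discontinuation; values from days 631-714 are not stated regressors. This is a reading of the endpoint left unshown, not an error in the primary analysis.

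All subject counts rest on the assumed 10-20% evenly spread discontinuation. A reader might infer a biased treatment difference, but neither its direction nor its size can be derived: the documents give no discontinuation rate by arm and no pattern of late eGFR falls. Items (a) and (b) should be corrected; (c) supports an optional addition.

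**What to change.** 1. **SAP 6.2.3.** Exclude discontinuation-visit values of fasting glucose, fasting neutral lipids and the fasting urine glucose/creatinine ratio unless a fast of at least 10 hours is documented. The documents available do not say that fasting status is recorded; if it is not, exclude all such values. Cost: wording, and the loss of a few values.
2. **SAP 6.2.1.** State that an eGFR from the follow-up period is not used as a Week 104 value. Cost: one sentence.
3. **SAP 7.6.1 and 7.6.2.1, optional and supplementary only.** Keep the primary analysis. Classify subjects with a Week 104 value by it, and discontinuers without one by the eGFR measured at the discontinuation visit. Leave those with neither imputed as in 6.2.2. Combine by Rubin's rule and present the difference (placebo minus TA-7284) with the Farrington-Manning interval. Cost: one table for each of the two endpoints, from data already collected. Downside: an early discontinuation value understates the two-year decline, so this analysis should not replace the primary one.
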